10.2.4 Stratification Factors

There is no stratification in this trial.

10.2.5 Analysis Plan

The primary endpoint of the study is to determine the maximum tolerated dose (MTD) of reirradiation using hypofractionated IMPT for patients with locoregionally recurrent rectal cancer. The MTD will be defined as the dose associated with a 35% probability of dose-limiting toxicity (DLT) as described above.

The secondary endpoints are clinical complete response rate, freedom from locoregional progression (FFLP), overall survival (OS), progression-free survival (PFS), PRO QOL, and adverse events as defined by CTCAE version 5.

Descriptive statistics will be calculated on all variables. Frequencies will be computed for all binary/categorical variables, and continuous variables will be summarized using medians, quartiles, and ranges. Next all variables will be compared with the historical data using Chi-square tests for binary/categorical variables and t-tests for continuous variables.

All the survival events will be measured from the end of radiation therapy and subjects who do not develop events will be censored at the last follow-up. Patients with distant metastasis will be continued to be followed for locoregional tumor recurrence until the last follow-up or time of death whether. Death will be analyzed as a competing cause in FFLP. Kaplan-Meier curves will be performed to compare the freedom from locoregional progression (FFLP), progression-free survival (PFS) and overall survival (OS). Cox proportional hazard model with log-rank test will be used to explain the correlation between explanatory variables and survival times.

Version 09/11/2025 page 43 of 63

Adjusted hazard ratios (HR) and the corresponding 95% confidence intervals (CI) will be reported.

PRO QOL questionnaires (Appendix B and C) will be tabulated for each domain and summed to generate a composite global QOL score. Repeated measures ANOVA will be used to compare QOL scores collected at baseline and at 1-2 weeks, 3 months, 6 months, 9 months, and 12 months after RT.

Adverse events or treatment-related toxicities will be classified as acute (<3 months after RT completion) toxicities and late (3-12 months after RT completion) toxicities. Adverse events, along with their maximum grade and relationship to study treatment, will be tabulated and assessed descriptively for patterns of occurrence. Frequency tables will include frequencies and percentages at the patient level as well as at the AE level. Point estimates for proportions will be reported, along with small sample confidence interval estimates.

All analyses will be performed in R (RFoundation for Statistical Computing) or in SAS (SAS Institute, Inc.; Cary, NC).

Version 09/11/2025 page 44 of 63

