1.2 Reirradiation

Given the clinical challenges and limitations with salvage surgery, investigators have explored pelvic reirradiation with and without salvage surgery and chemotherapy in the setting of LRRC (22–24). Reirradiation of the pelvis poses significant risks due to the cumulative effects on the organs at risk (OARs), such as the residual rectum, bladder, small, and large bowel, and the maximum lifetime dose to OARs for which toxicities outweigh the benefits of local-regional control remain undefined (25). Studies have reported reirradiation using conventional fractionation (1.8-2.0 Gy/fraction daily) (26–32) and hyperfractionation (1.2-1.5 Gy/fraction twice a day) (26, 33–37).

Version 09/11/2025 page 12 of 63

Metanalyses of these reirradiation studies showed pooled 1-, 2-, and 3-year OS rates for patients who received reirradiation and surgery were 86%, 72%, and 52%, respectively (24). The pooled grade ≥3 acute and late complication rate was 12% in patients who underwent reirradiation alone and was 26% in patients who underwent reirradiation and surgery (24). However, the 3-year OS was merely 24% in patients who received reirradiation alone (24). Since the low doses of 30-45 Gy delivered via conventional or accelerated hyperfractionation with photon therapy are generally insufficient to eradicate gross disease and are considered to the be palliative without salvage surgery (24).

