10.2 Simulation and Sample Size Calculations

The TITE-CRM manual details methods for utilizing trial simulation in order to obtain estimated posterior probabilities on toxicity estimates. We utilized the simulation program to determine the efficacy of our trial and obtain estimates for needed sample size. While there is no exact power calculation for this type of trial, the effectiveness of the trial's sample size can be determined by looking at the stability of the posterior probability under different prior probabilities.

We ran 1000 simulations under various increasing and decreasing prior probability estimates utilizing the previously described rules and assumptions for this trial and saw sufficient stability in posterior probability estimates with a sample size of 20 patients with a run-in of 6 patients. Simulations showed that approximately 95% of the time the trial will come to completion and the MTD will fall between the 3rd and 5th dose level 89% of the time. Therefore, we will use a fixed sample size of 20 patients for this trial. The posterior probability distribution of these 1000 simulations follow in the next table.

Version 09/11/2025 page 41 of 63

Dose Level	Estimated	Mean
	initial	Posterior
	toxicity	toxicity (SD)
d-1	0.25	0.328 (0.434)
1	0.30	0.38 (0.453)
(Starting		
Dose)		
2	0.35	0.43 (0.463)
3	0.40	0.479 (0.464)

Summary of simulation with estimated posterior probabilities. SD, Standard Deviation

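### Section 10.2.5 plans chi-square and t-tests of every variable against historical data that are never identified; the p-values could not be read as treatment effects

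*Combined protocol and SAP*

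**What the plan says.** After the descriptive summaries, section 10.2.5 adds: "Next all variables will be compared with the historical data using Chi-square tests for binary/categorical variables and t-tests for continuous variables". It does not say which data these are, how many patients they cover, whether the tests are one-sample or two-sample, or at what level they are judged.

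The same section lists six secondary endpoint families: "The secondary endpoints are clinical complete response rate, freedom from locoregional progression (FFLP), overall survival (OS), progression-free survival (PFS), PRO QOL, and adverse events". Most have their own methods. FFLP, PFS and OS get Kaplan-Meier and Cox analyses with censoring, and death is treated as a competing cause for FFLP. Quality of life gets repeated measures ANOVA. Adverse events are tabulated descriptively, and "Point estimates for proportions will be reported, along with small sample confidence interval estimates".

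Section 10.2 sets the sample size: "Therefore, we will use a fixed sample size of 20 patients for this trial". It concedes, "While there is no exact power calculation for this type of trial", and rests the number on TITE-CRM simulation: "We ran 1000 simulations under various increasing and decreasing prior probability estimates". No historical comparison enters that reasoning.

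The nearest candidates for a comparator are pooled literature figures in section 1.2. There the grade 3 or higher complication rate "was 12% in patients who underwent reirradiation alone and was 26% in patients who underwent reirradiation and surgery". One-year OS of 86% is given for reirradiation with surgery, and three-year OS of 24% for reirradiation alone. None of these is designated as the comparator in section 10.2.5.

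**The concern.** A test against historical data answers a question about treatment only if the historical group is known, comparable and fixed before the results are seen. None of this is secured here.

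- **Source.** With no source named, the comparator could be chosen after the data are in. The protocol itself describes suitable data as scarce or absent: section 1.4 notes how little prospective evidence exists on proton reirradiation in rectal cancer, and the section 2 table says much the same of patient-reported quality of life, SCCA and inflammatory markers.
- **Comparability.** The section 1.2 rates come from conventional or hyperfractionated regimens, whereas this trial gives five fractions at 25 to 40 Gy in total. Salvage surgery can occur (section 5.3.4.1), and section 6 keeps toxicities definitely or very probably due to it off the toxicity form, so toxicity may be captured differently from a published series.
- **Multiplicity.** The sentence covers every variable, and nothing limits the number of tests.
- **Fit with the rest of the section.** Read literally, it sends adverse events to significance tests although they are to be described, and survival times to tests that ignore censoring.

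At stake is the secondary and exploratory reporting. It has some reach, because the section 2 table says that survival results from this trial would be combined with those of any later phase II study.

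**Working it through.** **Inputs from the documents.** n = 20 (section 10.2); six secondary endpoint families (section 10.2.5); historical rate of 12% for reirradiation alone (section 1.2), used only as an example. QLQ-C30 scores: 5 functional + 1 global + 3 symptom + 6 single items = 15 (section 1.5.1). QLQ-CR29 scores: 4 scales + 19 single items = 23, some specific to sex or stoma (section 1.5.2). Total 15 + 23 = 38 at one time point.

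**Assumptions.** Two-sided level 0.05. The plan gives none for these tests; its closest text is "Adjusted hazard ratios (HR) and the corresponding 95% confidence intervals (CI) will be reported". The plan has no figure of its own to reproduce: it states no power or error rate for the comparisons, and the 20 cannot be re-derived because the simulation scenarios are not listed.

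**1. Effect of case mix alone.** Take a one-sample chi-square test of x events in 20 against a fixed rate of 12%. The statistic is (x − 20 × 0.12)² / (20 × 0.12 × 0.88) = (x − 2.4)² / 2.112, and rejection needs more than 3.84.

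- x = 5 gives 3.20: not rejected.
- x = 6 gives 6.14: rejected.
- x = 0 gives 2.73: not rejected.

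The test therefore rejects exactly when x is 6 or more. Binomial probabilities of that:

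| True rate in trial population | Difference due to case mix | P(reject) |
|---|---|---|
| 12% | 0 | 2.6% |
| 17% | 5 points | 11% |
| 22% | 10 points | 27% |
| 27% | 15 points | 46% |

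No treatment effect is involved in any row. The first row shows that small counts do not inflate the size at this rate. Over other historical rates from 5% to 50% the one-sample size ran from 3.2% to 7.5%, so small-sample error is a minor issue.

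**2. Multiplicity.** For k independent tests of true nulls, P(at least one false positive) = 1 − 0.95^k.

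| k | P(at least one) |
|---|---|
| 6 (one per secondary family) | 26.5% |
| 10 | 40.1% |
| 14 | 51.2% |
| 20 | 64.2% |
| 38 (quality-of-life scores, one time point) | 85.8% |

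The scores will be correlated. Simulating 38 equally correlated z-tests gives 73% at correlation 0.3, 56% at 0.5 and 28% at 0.8.

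**3. Power.** For 20 trial patients against an assumed historical group of 20 to 500, power to separate 12% from 26% is 20% to 47%. For 12% against 35% it is 40% to 77%.

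**4. What estimation would show.** Exact (Clopper-Pearson) 95% intervals: 2/20 = 10% (1.2% to 31.7%); 4/20 = 20% (5.7% to 43.7%); 7/20 = 35% (15.4% to 59.2%); within a dose level, 2/6 = 33% (4.3% to 77.7%).

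**The case against.** The strongest reply is that nothing important turns on this sentence. The MTD comes from the TITE-CRM, the secondary objectives are worded as estimation or evaluation, and section 2 ties further trials to tolerability. That stands. A reader might infer that the trial's efficacy and toxicity conclusions rest on these tests; the documents do not support that, because survival, quality of life and adverse events each have their own analysis.

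Other tempting readings also fail:

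- **That the tests are unplanned.** They are written into the plan; what is missing is their specification.
- **That the plan pools dose levels.** Section 10.2.5 does not say so. It gives no analysis by dose, and section 10.2.4 says there is no stratification, so pooling is an inference from silence. What can be said is that no adjustment for dose is specified.
- **That survival will be analysed by t-test.** Censored-data methods follow in the next paragraph. The conflict arises only if the reference to all variables is taken literally.
- **That false positives are more likely than not.** This needs about 14 or more independent true nulls at 5%. Six tests give 26.5%, and 38 strongly correlated ones give 28%. For baseline variables a rejection may reflect a real difference in case mix.
- **That the tests cannot be run without patient-level historical data.** One-sample forms need only a published rate or mean.

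What the reply leaves unanswered is the absence of a comparator, a significance level and any adjustment.

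**Conclusion.** The point holds in a limited form. Carried out as written, the sentence would produce p-values in which a treatment effect cannot be separated from case mix, salvage surgery or dose mix, with no control of their number. Non-comparability is the main fault: differences of 5 to 15 points in case mix alone give rejection rates of about 11% to 46% against a 12% rate, assuming a one-sample test at 5%. Multiplicity comes second, at about 27% for 6 independent tests, 64% for 20, and 28% to 86% for 38 scores depending on correlation, assuming a 5% level and true nulls throughout. The effect is confined to secondary and exploratory reporting. The change should be made, but the primary design does not depend on it.

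**What to change.** Delete the sentence from section 10.2.5. Keep the planned Kaplan-Meier, Cox and competing-risk analyses and the quality-of-life analysis. Report proportions with exact 95% confidence intervals, and 12-month survival with Kaplan-Meier 95% confidence intervals, both overall and by dose level. This extends the small-sample intervals that the section already promises.

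If published rates are wanted for context, show those in section 1.2 beside the estimates, without p-values and labelled by population: 12% toxicity for reirradiation alone; 26% toxicity and 86% one-year OS for reirradiation plus surgery. State that section 1.2 gives no one-year OS for reirradiation alone, and that its 24% figure is at three years, beyond this trial's 12-month follow-up. The 86% is therefore not a like-for-like benchmark.

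The cost is a wording change and somewhat less analysis. The sponsor gives up nominal p-values against historical data, and the by-dose intervals will be wide.

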5.8 Duration of Follow-up

Patients will be followed for 12 months following the completion of IMPT or until death, whichever occurs first. Patients removed from study for unacceptable adverse events will be followed until resolution or stabilization of the adverse event. Follow-up is described in Section 5.3.4. Patients will be followed by office visits, phone calls, and review of medical record. Any additional follow-up and imaging will be obtained off-study as per routine clinical policies of the treating physician.

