In order to account for the possibility of poor initial outcomes we will employ a run-in of 6 patients, meaning that the minimum number of treated patients will be 6. If after these 6 patients, or any other time during the trial, the lowest dose level has a posterior probability higher than 40% then the trial will stop.

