10.2.3 Replacement of Subjects that are not Evaluable

Patients who withdraw from the dose escalation component of the trial for any other reason than toxicity and who have not already developed a dose-limiting toxicity (DLT) at that point will be replaced by recruiting another patient at the same dose level.

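### Adjusted Cox hazard ratios are promised from about 20 patients with no covariates named; event counts are likely too low to support multivariable estimates

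*Combined protocol and SAP*

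**What the plan says.** Section 10.2.5 (Analysis Plan) covers FFLP, PFS and OS. It states: "Cox proportional hazard model with log-rank test will be used to explain the correlation between explanatory variables and survival times", and then: "Adjusted hazard ratios (HR) and the corresponding 95% confidence intervals (CI) will be reported". It does not say which explanatory variables enter, how many, how the model is fitted, how many events are expected, or whether the hazard ratios are descriptive.

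The sample size comes from the dose-finding simulation in Section 10.2: "we will use a fixed sample size of 20 patients for this trial". Section 10.1.2 allows an early stop, "meaning that the minimum number of treated patients will be 6". Section 10.2.3 says that certain withdrawals "will be replaced by recruiting another patient at the same dose level", so the number treated could slightly exceed 20.

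On follow-up, Section 5.8 says: "Patients will be followed for 12 months following the completion of IMPT or until death, whichever occurs first". Section 10.2.5 adds that "subjects who do not develop events will be censored at the last follow-up".

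**The concern.** A hazard ratio can only be adjusted if the model holds at least two covariates. The information in a Cox model comes from events, not patients, and 20 patients followed for one year will supply few. With so few events, a hazard ratio can land far from 1 by chance alone. If all events fall in one category of a covariate, the estimate diverges. Because the covariates are left open, the number fitted can be chosen after the data are seen.

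What is at stake is the credibility of the secondary survival results and of the exploratory SCCA association. The dose decision is not involved.

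**Working it through.** **The plan's own figure.** The documents give no event count, covariate count or power for the Cox model, so there is nothing to reproduce. The figure of 20 was chosen for stability of the toxicity posterior.

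**Expected deaths by 12 months.** Section 1.2 gives two historical figures.
- Reirradiation alone: 3-year OS 24%. With a constant hazard (an assumption), 12-month OS = 0.24^(1/3) = 0.621, so deaths = 20 × (1 − 0.621) = 7.6 (binomial 5th to 95th percentile 4 to 11).
- Reirradiation plus surgery: 1-year OS 86%, so deaths = 20 × 0.14 = 2.8 (1 to 6).
- Half with surgery: (7.6 + 2.8)/2 = 5.2.

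The supportable range is about 3 to 8 deaths. The exploratory SCCA endpoint uses OS at 6 months. Under the first assumption that is 20 × (1 − 0.24^(1/6)) = 20 × 0.212, or about 4 deaths. PFS also counts progression; no rate is given, so 12 to 15 events are assumed.

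**Analytic check, one balanced binary covariate, 8 events.** SE(log HR) = 1/√(d·p·(1−p)) = 1/√(8 × 0.25) = 0.71.
- The 95% CI runs from HR/4.0 to HR × 4.0, a 16-fold span.
- With a true HR of 1, the chance of an estimate at or beyond 3 or 1/3 is 2 × [1 − Φ(1.099/0.707)] = 12%.
- Power for a true HR of 2 is 16%. By Schoenfeld's formula, 80% power needs 66 events; with 8 events only an HR of about 7.25 is detectable at that power.

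**Simulation.** n = 20, every true HR equal to 1, exponential survival, censoring at 12 months, ordinary partial likelihood. The entry is the percentage of trials in which at least one HR is 3-fold or more off (≥3 or ≤1/3) or the fit fails.

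| Setting | 1 covariate | 2 | 3 |
|---|---|---|---|
| About 7.6 deaths, balanced binary | 17% | 38% | 52% |
| About 7.6 deaths, continuous, HR per SD | 3% | 9% | 16% |
| About 12 PFS events, balanced binary | 8% | 18% | 34% |

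Repeat runs of the first cell give 17% to 19%. With 15 events and binary covariates, at least one HR is 3-fold or more off in about 5% (one covariate) and 26% (three). At about 7.6 deaths, the median one-covariate 95% CI spans about 20-fold for a binary covariate and about 5-fold for a continuous one. These simulated results are somewhat worse than the analytic ones because the number of deaths varies from trial to trial.

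**The low end.** With 86% survival and binary covariates, 42% of one-covariate fits and 64% of three-covariate fits fail. The first follows by hand. All deaths fall in one group with probability 2 × 0.5^d. Averaged over d ~ Binomial(20, 0.14), with trials without deaths counted once, this is 2 × 0.93^20 − 0.86^20 = 0.468 − 0.049 = 0.42. With exactly 3 deaths it is 2 × 0.5³ = 25%.

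**False significance.** The per-covariate rate at p < 0.05 is about 2% to 6%. The chance of at least one such result among three covariates is about 10% (binary) to 15% (continuous) at about 8 deaths.

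**The case against.** Several counter-arguments stand in part.

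- **The intervals will show the uncertainty.** True. The same sentence promises 95% CIs, and per-covariate type I error is near nominal. A reader might infer that the plan would produce many false-significant findings; the calculations do not support that for a single covariate. What remains is the multiplicity of an open covariate list, and fits that fail.
- **The markers the protocol names are continuous.** SCCA (Section 2) and CRP and LDH (Section 1.6) are serum levels. Expressed per SD they behave much better: 3% with one covariate, against 17% for a binary one. A reader might infer that large spurious hazard ratios are common whatever is fitted. That holds for several binary covariates, not in general. Because the plan names no covariates for the Cox model, it does not secure the better case.
- **PFS will have more events.** True, and it helps, but three binary covariates still give about one trial in three with a 3-fold error at 12 events. FFLP cannot have more events than PFS, since it leaves out distant progression and death.
- **The analyses are secondary.** True. Section 2 calls the survival estimates preliminary and lists the SCCA association as exploratory.
- **No fitting method is stated.** True. Ordinary partial likelihood is assumed here because an unqualified Cox model is normally fitted that way.

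**Conclusion.** The point holds as a minor, cheap improvement. The plan commits to adjusted hazard ratios with covariates unnamed and unlimited, in a trial whose event counts are unlikely to support a multivariable model. The size depends on three things the documents leave open: the number of events, the type of covariate and how many are fitted. Across two or three covariates, the chance of at least one 3-fold error or failed fit runs from about 9% (two continuous) to 52% (three binary) at about 7.6 deaths, and is higher at about 3 deaths.

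A reader might take about 8 deaths as the plan's own expectation. It is not: the plan assumes no survival rate, and 8 is the top of a range that rests on a historical 3-year figure and a constant hazard. Fewer deaths would make the instability worse. Nor is 20 a strict ceiling, given replacement, and early stopping could leave far fewer; neither changes the conclusion. The MTD is not affected.

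**What to change.** In Section 10.2.5, delete the sentence "Adjusted hazard ratios (HR) and the corresponding 95% confidence intervals (CI) will be reported" and replace the Cox wording along these lines:

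- Report Kaplan-Meier estimates for OS and PFS, and cumulative incidence for FFLP with death as the competing event, each with 95% CIs, for all patients together. Splitting 20 patients over up to four dose levels would be very imprecise.
- If associations such as SCCA with PFS or OS are explored, fit one pre-named covariate at a time, kept continuous where possible, using Firth-penalised Cox regression with profile-likelihood CIs.
- State the number of events beside each estimate and label the result hypothesis-generating.

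The penalty prevents divergent estimates; it does not cure the imprecision, and the text should say so. The cost is a few sentences of SAP wording, with no extra patients or data. The sponsor gives up multivariable hazard ratios, which no stated objective requires: the survival objectives ask for medians and 12-month outcomes, and the SCCA objective asks for an association that a one-covariate fit can address.

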1.5.1 EORTC QLQ-C30 Quality of Life of Cancer Patients

The EORTC QLQ-C30 Quality of Life of Cancer Patients is a validated, widely utilized QOL questionnaire in general oncology for adult patients (79, 80). The EORTC QLQ-C30 consists of a 30-question questionnaire, which assesses patient well-being with five functional scales (the physical, role, emotional, cognitive, social, and global). It also includes three symptom scales (fatigue, pain, nausea/vomiting) and six single items (dyspnea, sleep disturbance, appetite loss, diarrhea, constipation, and financial impact) (79, 80). Single-item QL scores for overall physical condition (question 29), overall quality of life (question 30), and the global and social functioning scales have been shown to be prognostic for overall survival in adult patients with advanced malignancies (82)

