1.5.2 EORTC QLQ-CR29 Colorectal QOL

Developed in 2007 (83) as an update to QLQ-CR38 (84), the EORTC QLQ-CR29 questionnaire is a supplemental module designed to be delivered alongside the core

Version 09/11/2025 page 14 of 63

QLQ-C30 to assess QOL for patients with colorectal cancer.

The QLQ-CR29 contains 29 questions, including items in 4 scales (urinary frequency, blood/mucus in stools, stool frequency, body image) and 19 single items (urinary incontinence, dysuria, abdominal pain, buttock pain, bloating, dry mouth, hair loss, taste, anxiety, weight, flatulence, fecal incontinence, sore skin, embarrassment, stoma care problems, sexual interest for men, sexual interest for women, impotence, dyspareunia) (83). There are 11 items allocated for specific sub-populations, including males, females, and stoma patients. Scores of the QLQ-CR29 can be linearly transformed to provide a score from 0 to 100, with higher scores representing higher levels of functioning on the functional scales, greater degrees of symptomatology on the symptom scales and improved QOL on the global QOL scale (83).

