APPENDIX B: EORTC QLQ-C30 Quality of Life of Cancer Patients

EORTC QLQ-C30 (version 3)

Your birthdate (Day, Month, Year):

Please fill in your initials:

13. Have you lacked appetite?

14. Have you felt nauseated?

16. Have you been constipated?

15. Have you vomited?

We are interested in some things about you and your health. Please answer all of the questions yourself by circling the number that best applies to you. There are no "right" or "wrong" answers. The information that you provide will remain strictly confidential.

Too	day's date (Day, Month, Year): 31				
		Not at All	A Little	Quite a Bit	Very Much
1.	Do you have any trouble doing strenuous activities, like carrying a heavy shopping bag or a suitcase?	1	2	3	4
2.	Do you have any trouble taking a long walk?	1	2	3	4
3.	Do you have any trouble taking a short walk outside of the house?	1	2	3	4
4.	Do you need to stay in bed or a chair during the day?	1	2	3	4
5.	Do you need help with eating, dressing, washing yourself or using the toilet?	1	2	3	4
Du	rring the past week:	Not at All	A Little	Quite a Bit	Very Much
D u 6.	Were you limited in doing either your work or other daily activities?			_	
	•	All	Little	a Bit	Much
6.	Were you limited in doing either your work or other daily activities? Were you limited in pursuing your hobbies or other	All 1	Little 2	a Bit	Much 4
6. 7.	Were you limited in doing either your work or other daily activities? Were you limited in pursuing your hobbies or other leisure time activities?	All 1	Little 2 2	a Bit 3	Much 4
6.7.8.9.	Were you limited in doing either your work or other daily activities? Were you limited in pursuing your hobbies or other leisure time activities? Were you short of breath?	1 1 1	Little 2 2 2 2	3 3 3	Much 4 4 4
6. 7. 8. 9.	Were you limited in doing either your work or other daily activities? Were you limited in pursuing your hobbies or other leisure time activities? Were you short of breath? Have you had pain?	1 1 1 1	Little 2 2 2 2 2	3 3 3 3	Much 4 4 4 4

Please go on to the next page

2 3

2 3

2 3

Version 09/11/2025 page 54 of 63

During the past week:	Not at All	A Little	Quite a Bit	Very Much	
17. Have you had diarrhea?	1	2	3	4	
18. Were you tired?	1	2	3	4	
19. Did pain interfere with your daily activities?	1	2	3	4	
20. Have you had difficulty in concentrating on things, like reading a newspaper or watching television?	1	2	3	4	
21. Did you feel tense?	1	2	3	4	
22. Did you worry?	1	2	3	4	
23. Did you feel irritable?	1	2	3	4	

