24. Did you feel depressed?	1	2	3	4	
25. Have you had difficulty remembering things?	1	2	3	4	
26. Has your physical condition or medical treatment interfered with your family life? 1 2 3 4					
27. Has your physical condition or medical treatment interfered with your social activities? 1 2 3 4					
28. Has your physical condition or medical treatment caused you financial difficulties?	1	2	3	4	
For the following questions please circle the numb best applies to you	er bet	ween 1	l and	7 that	
29. How would you rate your overall health during the past week?					
1 2 3 4 5 6	7				
Very poor Ex	cellent				
30. How would you rate your overall quality of life during the past week?					
1 2 3 4 5 6	7				

© Copyright 1995 EORTC Quality of Life Group. All rights reserved. Version 3.0

Very poor

Version 09/11/2025 page 55 of 63

Excellent

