51. Have you had sore skin around your anal area?	1	2	3	4	
52. Did frequent bowel movements occur during the day?	1	2	3	4	
53. Did frequent bowel movements occur during the night?	1	2	3	4	
54. Did you feel embarrassed because of your bowel movement?	1	2	3	4	

During the past 4 weeks:	Not at All	A Little	Quite a Bit	Very Much
For men only:				
56. To what extent were you interested in sex?	1	2	3	4
57. Did you have difficulty getting or maintaining an erection?	1	2	3	4
For women only:				
58. To what extent were you interested in sex?	1	2	3	4

59. Did you have pain or discomfort during intercourse?

Version 09/11/2025 page 57 of 63

[©] QLQ-CR29 Copyright 2006 EORTC Quality of Life Group. All rights reserved. Version 2.1

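### Section 10.2.5 adds up questionnaire scales that run in opposite directions without reversing any, so the composite QOL score has no consistent direction

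*Combined protocol and SAP*

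**What the plan says.** The scoring rule is one sentence in section 10.2.5 (Analysis Plan): "PRO QOL questionnaires (Appendix B and C) will be tabulated for each domain and summed to generate a composite global QOL score". Repeated measures ANOVA then compares QOL scores at baseline and at five visits after radiotherapy. The section names no reversal, weighting or scoring manual, and neither does any other section.

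The protocol describes the scales as follows.

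- **Direction.** Section 1.5.2 mentions a linear transformation of QLQ-CR29 scores to 0-100 and says that high scores mean "higher levels of functioning on the functional scales, greater degrees of symptomatology on the symptom scales and improved QOL on the global QOL scale".
- **QLQ-C30 scales.** Section 1.5.1 lists "five functional scales (the physical, role, emotional, cognitive, social, and global"; the count given is five but six names follow. It continues: "It also includes three symptom scales (fatigue, pain, nausea/vomiting) and six single items".
- **QLQ-C30 items (Appendix B).** Questions 1-28 run from 1 (not at all) to 4 (very much) and ask about problems, for example "Do you need to stay in bed or a chair during the day". Questions 29 and 30 ask for ratings of overall health and overall quality of life ("30. How would you rate your overall" opens the last one), from 1 (very poor) to 7 (excellent).
- **QLQ-CR29 items (Appendix C).** Question 56 for men is "To what extent were you interested in sex". Question 57 is "Did you have difficulty getting or maintaining an erection". Both use the same 1-4 answers.

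Section 5.4 counts a patient as evaluable for QOL with either questionnaire or both, at baseline and at least one later visit.

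**The concern.** A sum can be read as better or worse QOL only if all its parts point the same way. Here, loss of function lowers some terms while growing symptoms raise others, so the two can cancel. A flat composite could hide real deterioration, and a change in it could mean either improvement or harm. A test over time on such a score inherits the same ambiguity.

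Patient-reported QOL is a listed secondary endpoint, and section 2 says that little such data exist for these patients. The composite is the only summary score that the plan defines for it.

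**Working it through.** The plan gives no figure for the composite (no range, effect size, SD or power), so there is nothing to reproduce. The check applies the summing rule of section 10.2.5 to the scale counts and directions in the protocol.

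**1. Sum of domain scores, QLQ-C30**

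Inputs: *g* high-is-better scales and *b* high-is-worse scales or items. From section 1.5.1, *b* = 3 + 6 = 9, and *g* = 6 by the names listed or 5 by the count given. Each is scored 0-100; this is assumed for the QLQ-C30.

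| Quantity | Formula | g = 6 | g = 5 |
|---|---|---|---|
| Best possible health | 100g + 0b | 600 | 500 |
| Worst possible health | 0g + 100b | 900 | 900 |
| All scales worsen by 10 | -10g + 10b | -60 + 90 = +30 | -50 + 90 = +40 |
| Functional/global only worsen by 10 | -10g | -60 | -50 |
| Symptom scales/items only worsen by 10 | +10b | +90 | +90 |

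Cancellation: three functional scales worsening by 30 and all nine symptom scales or items worsening by 10 gives -3 × 30 + 9 × 10 = 0.

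As an illustration only, let each scale either worsen by 10 or stay the same, with at least one worsening, and weight all patterns equally. With *k* high-is-better and *m* high-is-worse scales worsening, the sum changes by 10(m - k).

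- g = 6: 2^15 - 1 = 32767 patterns. The sum rises in 22819 (69.6%), is flat in 5004 (15.3%) and falls in 4944 (15.1%).
- g = 5: 2^14 - 1 = 16383 patterns. The sum rises in 12911 (78.8%), is flat in 2001 (12.2%) and falls in 1471 (9.0%).

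**2. Sum of raw items, QLQ-C30 (Appendix B)**

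- Best health: 28 × 1 + 2 × 7 = 42.
- Worst health: 28 × 4 + 2 × 1 = 114.
- Possible range: 28 × 1 + 2 × 1 = 30 to 28 × 4 + 2 × 7 = 126.

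Neither end of the possible range is best or worst health. Questions 29 and 30 both falling from 7 to 1 moves the total by -12. Twelve of the other items each worsening by one point moves it by +12, so the two changes together leave it flat.

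**3. QLQ-CR29**

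Section 1.5.2 itself describes opposing directions for this questionnaire, and questions 56 and 57 show them among the items if more sexual interest is taken as better. One composite per questionnaire therefore does not remove the conflict.

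The raw items also differ between patients: those with a stoma answer questions 49-55 and the others 49-54, question 48 is yes/no, and 56-59 depend on sex.

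The protocol does not say which of the 4 scales and 19 single items are functional. Assuming 0 to 6 of them are, and that 20 to 23 apply to a given patient, adding them to the six-plus-nine QLQ-C30 sum gives:

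- best health between 600 and 1200: 100 × (6 + 0) to 100 × (6 + 6);
- worst health between 2300 and 3200: 100 × (9 + 20 - 6) to 100 × (9 + 23 - 0).

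The functional and global terms still pull against the rest.

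**4. One sum across both forms**

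A patient who is evaluable under section 5.4 with only one questionnaire has no defined value.

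**5. Check of the remedy**

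Replacing each of the nine QLQ-C30 symptom scores by 100 minus the score gives best health 15 × 100 = 1500 and worst 0. A 10-point worsening on every scale then moves the sum by -150, and worsening on any subset lowers it.

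**The case against.** The best reply is that section 10.2.5 is silent on reversal and does not forbid it. The instruments are described as established and their papers are cited, so staff might apply standard scoring. That is possible, but the plan does not say so. The only transformation it describes, in section 1.5.2, leaves symptom and functional scales opposed. The summed phrase could also mean adding items within a domain, but the stated product is one composite global score, which makes that the weaker reading.

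A second reply is that the raw-item total mostly means higher-is-worse: 28 of 30 items agree and can move it by 28 × 3 = 84 points, against 2 × 6 = 12 for questions 29 and 30. This is fair, and it makes the raw-item version milder. It does not remove the conflict, because the two items that oppose the rest are the overall ratings of health and quality of life.

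Three limits stand.

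- The 600 and 900 figures rest on assumed 0-100 scoring of the QLQ-C30.
- Nothing in the protocol supports equal weighting of the worsening patterns. Those percentages only illustrate; the change of sign does not depend on them.
- No QOL hypothesis or dose decision hangs on the composite. The point about a patient with one form applies only if a single sum spans both questionnaires.

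**Conclusion.** The concern holds. Section 10.2.5 gives a summing rule, section 1.5.2 says the summed scales run in opposite directions, and nothing in the protocol aligns them. Under 0-100 domain scoring of the QLQ-C30, worst health outscores best health (900 against 600, or against 500 with five high-is-better scales). Worsening can move the sum by anything from -60 to +90 in the simple 10-point cases. Under raw-item scoring the distortion is smaller, but questions 29 and 30 still oppose the other 28.

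This should be corrected before any QOL analysis. It is confined to the composite and to tests on it.

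**What to change.** In section 10.2.5:

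1. Delete the unreversed sum.
2. Analyse each QLQ-C30 and QLQ-CR29 scale separately and state its direction.
3. Use QLQ-C30 questions 29 and 30 as the global QOL score.
4. If a composite is still wanted, reverse all scales to one direction first, form it separately for each questionnaire, and say how stoma-specific and sex-specific items are handled.

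The cost is SAP wording and a few more tables. Questionnaires, visits and software stay the same. What is lost is a single number across both questionnaires.

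A separate, optional improvement, which corrects no error: replace the repeated measures ANOVA with a linear mixed model, with visit as a categorical effect and a simple covariance. A random patient intercept needs 2 variance parameters, whereas an unstructured matrix over six visits needs 6 × 7 / 2 = 21, for 20 patients. Use all available forms from patients evaluable under section 5.4, and report the numbers alive and responding at each visit.

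Deaths by 12 months are likely. Section 1.2 gives 3-year survival of 24% after reirradiation alone and 1-year survival of 86% with surgery. As a rough guide, assuming a constant hazard for the first figure, that is 20 × 0.24^(1/3) = 12.4 to 20 × 0.86 = 17.2 of 20 patients alive. The mixed model does not resolve truncation by death, so results should be described as applying to patients alive at each visit.
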